#### 4.7.3 Additional safety assessments

##### 4.7.3.1 Laboratory variables, vital signs and electrocardiograms (ECGs)

The following laboratory variables, vital signs and electrocardiogram (ECG) variables will be analyzed. They will be converted into standard international units.

- Hematology and coagulation:
  - Red blood cells and platelets and coagulation: hemoglobin, hematocrit, red blood cell (RBC) count, platelet count, prothrombin time (expressed as international normalized ratio [INR]) and activated partial thromboplastin time (aPTT),
  - White blood cells: white blood cell (WBC) count, neutrophils, lymphocytes, monocytes, basophils and eosinophils.
- Clinical chemistry:
  - Metabolism: glucose, total protein, and albumin,
  - Electrolytes: sodium, potassium, and corrected calcium. Corrected calcium (mmol/L) will be derived using the following formula: measured total calcium (mmol/L) +  $0.8 \times 0.25 \times (4.0 - [\text{serum albumin } \{g/L\} \times 0.1])$ , where 4.0 represents the average albumin level,
  - Renal function: creatinine, blood urea nitrogen (BUN) and urea,
  - Liver function: alanine aminotransferase (ALT), aspartate aminotransferase (AST), alkaline phosphatase (ALP), lactate dehydrogenase (LDH), total and direct bilirubin,
  - Circulating carcinoembryonic antigen (CEA).

- Urinalysis:
  - Urine dipstick: proteins,
  - Urinalysis: proteins assessed on 24 hour urine collection.
- Vital signs: heart rate, systolic and diastolic blood pressure, weight and ECOG Performance Status (PS).
- ECG variables: PR, QRS, QT and corrected QTcF (according to Fridericia).
- $QTcF=QT/RR^{0.33}$ .

where RR interval (in seconds) = 60/HR, and HR = heart rate in beats per minute (from the ECG form).

Data below the lower limit of quantitation/detection limit (LLOQ) will be replaced by half of the LLOQ, data above the upper limit of quantification will be replaced by ULOQ value.

For hematological parameters and some selected coagulation and biochemistry parameters, Sanofi sponsor generic ranges (LLN, ULN) are defined and will be used for grading (see list of parameters in [Section 5.4](#)). For other coagulation and biochemistry parameters, grading will be derived using local laboratory normal ranges.

### **Quantitative analyses**

For vital signs and ECG variables above, descriptive statistics for results and changes from baseline will be provided for each planned visit, and the worst value (minimum and/or maximum value depending on the parameter) during the treatment-emergent period. These analyses will be performed using local measurements.

For QRS and QTcF variables, blood pressure, and heart rate, mean changes from baseline with the corresponding standard error will be plotted over time.

### **Analyses according to potentially clinically significant abnormalities (PCSA) and NCI grading**

For laboratory variables, analyses according to NCI grading will be made based on NCI-CTCAE Version 5.0. In addition, for laboratory variables for which the NCI-CTCAE scale is not applicable, such as vital signs and ECG variables, PCSA analyses will be performed based on the PCSA list currently in effect at Sanofi at the time of the database lock.

Analyses according to PCSA and NCI grading will be performed based on the worst value during the treatment-emergent period, using all measurements (either local or central, either scheduled, nonscheduled or repeated).

QTcF prolongation will be graded according to NCI-CTCAE version 5.0. The frequency of participants each grade of QTcF prolongation during the on-treatment period will be summarized. For participants with multiple occurrences of QTcF prolongation during the treatment, the maximum grade per participant will be used.

For laboratory variables, vital signs and ECG variables above, the incidence of participants with at least one PCSA during the treatment-emergent period will be summarized regardless of the baseline level and according to the following baseline status categories:

- Normal/missing
- Abnormal according to PCSA criterion or criteria

The number (%) of participants with QTcF abnormality worsening during the on-treatment period (worst value per participant) will be displayed.

For laboratory variables graded by NCI-CTCAE,

- The number (%) of participants with abnormal laboratory tests at baseline will be presented by grade.
- The number (%) of participants with an abnormal laboratory test during the treatment-emergent period will be summarized by grade. When appropriate, the number (%) of participants with abnormality of any grade and with Grade 3-4 abnormalities will be provided.
- For liver function test abnormalities, the baseline status will be provided according to multiples of the upper limit of normal (ULN) for each test.

For laboratory variables graded neither by NCI-CTCAE nor by PCSA, the number (%) of participants with laboratory test results outside normal ranges will be provided.

#### ***Additional analyses for drug-induced liver injury***

The following additional analyses will be performed for drug-induced liver injury:

- For each liver function test (eg, ALT), participants having experienced a PCSA will be summarized considering worst on-treatment value.
- An Evaluation of Drug-Induced Serious Hepatotoxicity (eDISH)-like plot of peak bilirubin/ULN versus peak or /ULN will be provided. The graph will be divided into 4 quadrants with a vertical line corresponding to  $3 \times$  ULN for ALT/AST, and a horizontal line corresponding to  $2 \times$  ULN for total bilirubin.
- For each liver function test (eg, ALT), participants having experienced a PCSA (eg,  $ALT > 5 \times$  ULN) will be summarized using the following categories: Returned to baseline PCSA status (or returned to value  $\leq$  ULN in case of missing baseline) before last IMP dose, Returned to baseline PCSA status after last IMP dose, Never returned to baseline PCSA status, No assessment after elevation. This summary will be performed by categories of elevation ( $ALT > 3, > 5, > 10, > 20 \times$  ULN).

#### **4.7.3.2 Ocular examinations**

##### ***Schirmer test***

Participants reported Schirmer's test will be classified into 3 classes at baseline: normal ( $\geq 10$  mm), mild ( $< 10$  and  $> 5$  mm), severe ( $\leq 5$  mm). The worst classification between the laterality will be considered. A frequency table of the baseline status with and without anaesthetics will be provided for the participants with corneal events (CMQ) during the treatment-emergent period and for the participants without an event.

##### ***Visual acuity test***

Analyses are done on the best corrected visual acuity assessed using Snellen Chart method.

Frequency tables on best corrected visual acuity (BCVA) measured during on-treatment period will be performed separately on all participants and on participants who experienced at least one treatment-emergent corneal event:

- On the worst change from baseline: No worsening versus baseline (no line decrease), Worsening versus baseline 1 to 3 lines decrease versus baseline, or  $> 3$  lines decrease versus baseline).
- On the worst absolute value: No change versus baseline, Worsening versus baseline (BCVA equals to 20/40 or better, BCVA worse than 20/40 up to 20/200, BCVA 20/200 or worse).
- On the CTCAE worst vision decrease: BCVA equals to 20/40 or better or 1 to 3 lines decrease versus baseline, BCVA worse than 20/40 up to 20/200 or  $> 3$  lines decrease versus baseline, BCVA 20/200 or worse.
- For participants who had worsening versus baseline on BCVA (at least one line decrease), the worst outcome on the last BCVA value will be displayed: Recovered to baseline, Not recovered to baseline, Lost to follow-up or dead with ongoing corneal events.

Of note, a participant will be considered as lost to follow-up, if the participant discontinued the study and did not perform any follow-up visit.

A shift table of the category of the last BCVA value (Normal (20/20 or better), worse than 20/20 up to 20/40, worse than 20/40 up to 20/200 or 20/200 or worse) versus the category of the worst BCVA value (20/40 or better, worse than 20/40 up to 20/200, 20/200 or worse) will be performed for participants who experienced at least one treatment-emergent corneal event.

For the summary table on participants who experienced at least one treatment-emergent corneal event, the worst value and the worst change from baseline are measured during any of the treatment-emergent corneal events experienced by the participant (between start date and end date of the corneal events). For the summary table on all participants, all on-treatment BCVA values are considered.

The worst classification between the laterality is considered for the worst value, the worst change from baseline and the last separately even if not measured on the same eye. If the worst absolute value is the same for both eyes, then the eye with the worst change from baseline is considered, and if identical, then the eye with the worst last value is considered.

Participants whose baseline visual acuity had been reported in naked eye instead of BCVA (ie whenever baseline value was worse than the values reported during the during the treatment period/ treatment-emergent corneal events) will be excluded from this analysis.

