	Grade 3-4 Severe Eg, symptomatic bronchospasm, urticaria lesions covering $>30\%$ BSA, hypotension, angioedema.	Interrupt ramucirumab infusion and prematurely definitively discontinue ramucirumab	Interrupt tusamitamab rvtansine infusion and prematurely discontinue tusamitamab rvtansine and consider infusion delay.	Give diphenhydramine 50 mg IV and/or dexamethasone 10 mg IV and/or epinephrine and any required treatment per investigator judgement.
Ocular toxicity: Keratopathy/keratitis ^b associated with tusamitamab rvtansine	Grade 1 - Asymptomatic Corneal lesions only observed on routine ocular examination and not requiring topical treatment.	Administer ramucirumab at same dose, and same day as tusamitamab rvtansine	Next infusion of tusamitamab rvtansine at the same dose, with or without cycle delay, depending on the recommendation from the ophthalmologist (nature and extent of the lesion).	Standard ocular examination is planned as recommended by the ophthalmologist.
	Grade 2 Symptomatic or requiring topical treatment (curative) or limiting instrumental activity of daily life. Moderate decrease in visual acuity (best corrected visual acuity 20/40 and better or 3 lines or less decreased vision from known baseline)	Administer ramucirumab as planned, and re-introduce tusamitamab rvtansine when recovery to Grade 1	1 st episode: Omit tusamitamab rvtansine until resolution to Grade 1 (asymptomatic) and restart tusamitamab rvtansine at the same dose. 2 nd episode: Omit SAR until resolution to Grade 1 (asymptomatic) and tusamitamab rvtansine dose reduction. 3 rd episode: depending on benefit risk, premature definitive discontinuation of tusamitamab rvtansine may be envisaged	Standard ocular examination weekly until resolution ^{c, d} . Start curative treatment per ophthalmologist recommendation. After resuming study treatment, participant should be followed with standard ocular examination by every 2 cycles, even asymptomatic during next 4 cycles. If no recurrence, standard process with follow-up with ocular symptom is resumed. Management of study drug upon recurrence to be discussed according to Grade of the event at recurrence, clinical benefit from study drug and recommendation from the ophthalmologist.

Event	Symptoms severity (Nadir) (NCI CTCAE v5)	Management of IMP dosing (ramucirumab))	Management of IMP dosing (tusamitamab rvtansine)	Supportive care guidelines

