	Grade 3 Symptomatic with marked decrease in visual acuity (best corrected visual acuity worse than 20/40 or more than 3 lines of decreased vision from known baseline, up to 20/200); corneal ulcer; limiting selfcare activity of daily life	Administer ramucirumab as planned, and re-introduce tusamitamab rvtansine when recovery to Grade 1	1 st episode: Omit tusamitamab rvtansine until resolution (asymptomatic) and restart tusamitamab rvtansine with dose reduction. 2 nd episode: definitive discontinuation of tusamitamab rvtansine.	Standard ocular examination weekly until resolution ^{c, d} . Start curative treatment per ophthalmologist recommendation. After resuming study treatment, participant should be followed with standard ocular examination by every 2 cycles, even asymptomatic during next four cycles. If no recurrence, standard process with follow-up with ocular symptom is resumed Management of study drug upon recurrence to be discussed according to Grade of the event at recurrence, clinical benefit from study drug and recommendation from the ophthalmologist
	Grade 4 Perforation or best corrected visual acuity of 20/200 or worse in the affected eye.	Administer ramucirumab as planned,	Definitive discontinuation of tusamitamab rvtansine.	Complete the corneal examination as recommended by ophthalmologist. Repeat the standard ocular examination weekly ^c until resolution ^d . Start curative treatment per ophthalmologist recommendation.
Conduction disorder associated with tusamitamab rvtansine	Grade 1 Mild symptoms	Administer ramucirumab as planned,	tusamitamab rvtansine administration to be continued upon decision by the Investigator and Sponsor, depending on the nature of the conduction disorder.	ECG performed once weekly until event resolution. Additional evaluations such as LVEF and Holter monitoring should be performed when relevant.
	Grade ≥2	Administer ramucirumab as planned,	Definitive discontinuation of tusamitamab rvtansine.	ECG to be repeated twice weekly until event resolution. Prompt cardiology consultation Additional evaluations such LVEF and Holter monitoring should be performed when relevant.

Event	Symptoms severity (Nadir) (NCI CTCAE v5)	Management of IMP dosing (ramucirumab)	Management of IMP dosing (tusamitamab rfvansine)	Supportive care guidelines

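### The SAP's CTCAE vision-decrease table has no row for participants without loss, its rows overlap, and worst and last values may come from different eyes, so descriptive ocular tables can misclassify participants

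*SAP*

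**What the plan says.** SAP Section 4.7.3.2, under the visual acuity test, plans frequency tables of best corrected visual acuity (BCVA) in the on-treatment period. They are produced once for all participants and once for those with at least one treatment-emergent corneal event. Three classifications are listed:

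- Worst change from baseline, whose first category is "No worsening versus baseline (no line decrease".
- Worst absolute value, which begins "No change versus baseline, Worsening versus baseline (BCVA equals to 20/40 or better".
- CTCAE worst vision decrease. Row 1 is "On the CTCAE worst vision decrease: BCVA equals to 20/40 or better or 1 to 3 lines decrease versus baseline". Row 2 starts "BCVA worse than 20/40 up to 20/200 or" and continues with a loss of more than 3 lines. The list ends "lines decrease versus baseline, BCVA 20/200 or worse", so row 3 is the last and no further row follows.

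On laterality, the worst value, the worst change and the last value are each classified from the worse eye, "even if not measured on the same eye". A further sentence picks a single eye when both eyes have the same worst absolute value. A shift table sets the category of the last BCVA against the category of the worst BCVA for participants with a corneal event. A separate summary classes participants who lost at least one line as recovered to baseline or not. The only exclusion is for baselines worse than the later readings, which are presumed to have been taken without correction.

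The CTCAE rows follow the keratopathy grades in Protocol Appendix 4 (Section 10.4). Grade 2 gives "best corrected visual acuity 20/40 and better or 3 lines or less decreased vision from known baseline" as the meaning of a moderate decrease. Grade 3 gives "best corrected visual acuity worse than 20/40 or more than 3 lines of decreased vision from known baseline, up to 20/200" as the meaning of a marked decrease. Grade 4 refers to acuity in the affected eye.

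**The concern.** The protocol applies its acuity limits to eyes in which vision has already fallen. The SAP takes over the limits without that condition and applies them to everyone with a reading, so good or long-standing stable vision is reported under a vision-decrease heading. Joining an absolute limit and a change limit with an *or*, without saying which prevails, also leaves the row open for many participants, and two programmers could produce different tables from the same data.

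The eye rule adds a separate problem. A participant's worst and last values need not come from the eye that the event affected, so an old defect in one eye can stand in for the other. The tie-break sentence, which selects one eye, does not fit easily with a rule that lets the three quantities come from different eyes.

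Protocol Section 2.3 names corneal toxicity as the main anticipated risk and describes it as reversible. These tables are part of the evidence on how far vision fell and whether it came back.

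**Working it through.** The plan gives no figure to reproduce; this is a check of stated categories. Let *v* be the Snellen denominator of the worst BCVA and *d* the lines lost from baseline. Taken literally:

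- Row 1: v ≤ 40 or 1 ≤ d ≤ 3
- Row 2: 40 < v ≤ 200 or d > 3
- Row 3: v ≥ 200

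The documents do not list the chart lines. I assume 20/20, 25, 30, 40, 50, 70, 100, 200 and 400, and vary this below. The counts are of logically possible cases, not expected numbers of participants.

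**1. No row for no loss.** With d = 0 the rows reduce to v ≤ 40, 40 < v ≤ 200 and v ≥ 200. Together these cover every acuity, so every unchanged reading meets at least one row. Of the 9 unchanged pairs, 4 meet row 1 only, 3 row 2 only, 1 row 3 only, and 1 (20/200) rows 2 and 3. The exclusion does not remove them, because the baseline is not worse than the later reading. Exclusion criterion E06 concerns corneal disorders and sets no acuity limit, so a baseline of 20/100 can be enrolled.

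**2. Overlap.** Nine lines give 9 × 10 / 2 = 45 pairs with the worst value no better than baseline. Of these, 20 meet one row, 22 meet two and 3 meet all three, so 22 + 3 = 25 of 45 overlap. Adding 20/60 and 20/80 gives 35 of 66; adding 20/15 instead gives 28 of 55. Leaving out the 8 pairs that end at exactly 20/200, 17 of 37 still overlap on the nine-line chart.

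| Baseline → worst | v | d | Rows met |
|---|---|---|---|
| 20/20 → 20/20 | 20 | 0 | 1 |
| 20/100 → 20/100 | 100 | 0 | 2 |
| 20/30 → 20/50 | 50 | 2 | 1 and 2 |
| 20/15 → 20/40 (chart with 20/15) | 40 | 4 | 1 and 2 |
| 20/100 → 20/200 | 200 | 1 | 1, 2 and 3 |

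**3. Eyes, CTCAE table.** Right eye 20/20 → 20/40 (d = 3); left eye stable at 20/100 (d = 0). Taken separately, the worst value is 100 (left) and the worst change is 3 (right), so the participant meets rows 1 and 2. The eye that worsened meets row 1 only.

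**4. Eyes, shift table.** In a participant with a corneal event, the right eye goes 20/20 → 20/80 → 20/20 and the left is stable at 20/100. Worst is 20/100 (left) and last is 20/100 (left), so both fall in the same category and no recovery shows. In the right eye alone, worst is 20/80 and last is 20/20, which is full recovery. Neither eye is ever better than its own baseline, so the exclusion does not remove this participant.

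**5. After the change proposed below (nine-line chart).** No worsening: 9. Row 3 (v = 200 or 400, d ≥ 1): 7 + 8 = 15. Row 2 (v = 50, 70 or 100, d ≥ 1): 4 + 5 + 6 = 15; no pair ending at 20/40 or better loses more than 3 lines on this chart. Row 1 (v = 25, 30 or 40): 1 + 2 + 3 = 6. The sum is 9 + 6 + 15 + 15 = 45, each pair in exactly one row.

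**The case against.** The strongest reply is that the intended reading is plain. The table is about the worst decrease, both documents count adverse events at the maximum grade, and the overlapping limits are inherited from the protocol's grades, so a sensible programmer would take the severest row. That is probably the intention. However, the acuity section uses the word *worst* for readings, changes and eyes, and nowhere says which row prevails. It also does not restrict the table to participants with a decrease.

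Three points on the other side stand. First, the worst-change and worst-value tables have explicit rows for no worsening or no change, so the information is not lost from the report. Second, not everyone enters the table. Acuity is measured at screening, when clinically indicated and at end of treatment. That last visit is 30 ± 5 days after the last infusion, while the on-treatment period stops at 30 days, so a symptom-free participant may have no on-treatment reading. Third, taking the worse eye is a disclosed convention, and the separate recovery summary can be read as comparing each eye with its own baseline. On that reading it gives the right answer for the shift-table example.

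A reader might infer that the overlap between Grade 2 and Grade 3 disturbs the DLT or AESI counts, where Grade 3 keratopathy is the threshold. The documents do not support this. DLTs are identified from the eCRF DLT page (SAP 4.3.1.1) after Study Committee confirmation (Protocol 4.1), and AESIs from an eCRF tick box (SAP Table 10). The BCVA tables feed neither. The grades also depend on symptoms, treatment need, daily activities and corneal ulcer, not on acuity alone.

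**Conclusion.** The point holds for descriptive ocular safety tables only. For participants with an on-treatment BCVA, the CTCAE table as written labels unchanged vision as a decrease. It leaves the row undetermined in more than half of the possible baseline/worst pairs on each chart tried (25 of 45, 35 of 66, 28 of 55). The shift table can conceal full recovery of the affected eye. The missing row and the double placement of 20/200 follow from the text alone; the overlap counts rest on the assumed chart lines. How many participants would be affected cannot be stated, because the documents give no distribution of baseline acuity.

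It should not be inferred that the report as a whole cannot separate no loss from loss, since the worst-change table does so correctly, or that the recovery summary is necessarily wrong. DLT, AESI and ORR results are untouched. Corneal events are also described by grade, onset, recurrence and outcome elsewhere in the SAP. The change is worth making because it concerns the main anticipated toxicity and is cheap.

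**What to change.** In SAP Section 4.7.3.2 only:

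- (a) Add a row for no worsening versus baseline to the CTCAE table, and require at least one line lost from that eye's own baseline for rows 1 to 3.
- (b) State that the most severe row met applies, and put exactly 20/200 in one row (the count above puts it in row 3). Under this rule every eye in row 1 is at 20/40 or better, which the table footnote should say.
- (c) Derive baseline, worst value, change and last value within each eye. Report the eye with the most severe category, ties broken by the larger line loss, and use that same eye in the shift and recovery summaries. Remove the present tie-break sentence.

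The cost is wording and minor programming. Laterality is already used in these analyses, so no new data are needed.

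Separately, the acuity wording of Grades 2, 3 and 4 in Protocol Appendix 4 overlaps in the same way, and the sponsor should reconcile it. How investigators grade events is not for the SAP to settle, and no grading rule is proposed here.

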8.2.2 Specific ocular tests

Specific complete ocular tests at baseline will include: assessment of ocular/visual symptoms and ocular exams including visual acuity, slit lamp under dilatation, and Schirmer's test.

Standard specific ocular tests include:

- Assessment of ocular/visual symptoms, (ie, blurred vision, photophobia, dry eye, etc) at each visit before each study intervention. Start and end dates of symptoms will be collected.
- Visual acuity at screening and whenever clinically indicated.
- Slit lamp under dilatation at screening and whenever clinically indicated.
- Schirmer's test at screening and whenever clinically indicated.

In participants with any ocular/visual symptom (eg, blurred vision, photophobia), complete ocular tests will be repeated at the time of the occurrence of the ocular toxicity, if any regardless of the grade. Thereafter, visual acuity, slit lamp examination under dilatation, and Schirmer's test will be repeated once weekly (if not recommended to have less frequent assessment by ophthalmologist based on lesion characteristics) until resolution to Grade 1. In case of recurrent ocular toxicity observed in subsequent cycles, visual acuity and slit lamp examination under dilatation, and Schirmer's test will be performed at the time of the event onset, then weekly until resolution to Grade 1.

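### The SAP infers a naked-eye baseline from better on-treatment acuity, so the result being tabulated decides who enters the visual-acuity tables

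*SAP*

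**What the plan says.** SAP 4.7.3.2, under the visual acuity heading, starts from a fixed measurement: "Analyses are done on the best corrected visual acuity assessed using Snellen Chart method". It then plans frequency tables of on-treatment acuity, once for everyone and once for participants with a treatment-emergent corneal event. One table classifies the worst change from baseline, and its first category is "No worsening versus baseline (no line decrease". For the version on everyone, "For the summary table on all participants, all on-treatment BCVA values are considered". The worst change, the worst value and the last value are each taken from the worse eye, and the three need not come from the same eye. A further shift table sets the last acuity category against the worst.

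The section ends by excluding a group from the analysis: "Participants whose baseline visual acuity had been reported in naked eye instead of BCVA (ie whenever baseline value was worse than the values reported". The first half gives the reason, a faulty baseline. The bracket then says how that group is recognised, and in full it reads "ie whenever baseline value was worse than the values reported during the during the treatment period/ treatment-emergent corneal events".

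The SAP cites no recorded correction status, source check or site query. It sets no minimum line difference and no per-eye rule. It does not say whether one better value is enough or all must be better. It asks for no count of those excluded and no table that keeps them.

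Acuity readings are sparse. Protocol 8.2.2 schedules them as follows: "Visual acuity at screening and whenever clinically indicated". The flow chart and Protocol 8.2.6.2 add an ocular evaluation at end of treatment.

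**The concern.** The reason given for the exclusion is a fact about baseline, but the test applied is a comparison with the outcome. A post-baseline result therefore sets the denominator of a table about that same result.

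The proxy errs in two ways. A correctly measured baseline is discarded when the participant truly improves, gets a new correction, or simply reads better on a repeat test. An uncorrected baseline stays in when later acuity is equal or worse, and the loss computed from it is too small.

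Corneal toxicity is the main anticipated risk of the drug (Protocol 2.3). These tables use the same line-loss, 20/40 and 20/200 cut-offs as the keratopathy grading in Protocol Appendix 4. With about 30 to 36 treated participants (SAP 1.1), a handful of exclusions visibly moves a percentage. A reader of the report would also have no means of seeing how many people had been removed.

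**Working it through.** **Denominator.** Safety tables use the all-treated population (SAP 4.7). SAP section 2 gives 225 prescreened with 80% and 20% failure rates: 225 × (1 - 0.80) × (1 - 0.20) = 36, which reproduces the planned maximum of 36 treated. SAP 1.1 gives 30 to 36. The documents give no figure for acuity loss, so every count below other than N is an assumption. The number with usable acuity data may also be smaller than N.

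**Reading A: baseline worse than all on-treatment values in both eyes.** Nobody excluded has lost a line. Let W be the number who lost at least one line and E the number excluded. The rate goes from W/N to W/(N-E), a factor of N/(N-E).

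| N | W | E | All kept | Under the rule |
|---|---|---|---|---|
| 30 | 6 | 3 | 20.0% | 6/27 = 22.2% |
| 30 | 6 | 5 | 20.0% | 6/25 = 24.0% |
| 30 | 4 | 6 | 13.3% | 4/24 = 16.7% |
| 36 | 9 | 4 | 25.0% | 9/32 = 28.1% |
| 36 | 9 | 7 | 25.0% | 9/29 = 31.0% |
| 36 | 9 | 11 | 25.0% | 9/25 = 36.0% |

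**Reading B: baseline worse than any value, or in either eye.** Let k of the E excluded have lost a line at another time or in the other eye. The rate becomes (W-k)/(N-E). It falls below W/N when k/E is greater than W/N. With N = 36, W = 9 (25.0%) and E = 7:
- k = 1: 8/29 = 27.6%
- k = 2: 7/29 = 24.1%
- k = 3: 6/29 = 20.7%

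The direction depends on who is excluded.

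**Does the rule catch correct baselines?** A simulation in Snellen lines gave every participant a properly corrected baseline, no true change and one on-treatment value, using one eye and rounding to whole lines.
- With an assumed test-retest SD of 0.5 line, the rule excludes 24%, and the share showing at least one line lost goes from 24% to 32%.
- With an SD of 1 line, it excludes 36%, and the share goes from 36% to 57%.
- With two on-treatment values and 25% of participants truly losing 3 lines, reading A moves the share from 52% to 57% (SD 0.5) or from 63% to 75% (SD 1).
- Under reading B with two values, 4% to 17% of participants are excluded although they lost a line. The share still rose in every setting simulated, so the falls in the count example are possible but not inevitable.

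The simulation contains no uncorrected baselines, so it shows only the false exclusions.

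**Does it miss uncorrected baselines?** Suppose the uncorrected baseline is d lines poorer than the corrected one, and the participant later truly loses L lines with correction. The recorded loss is L - d. If L is at least d, the baseline is not worse than the later value, so the participant stays in with a loss understated by d. If L is less than d, the participant is excluded, even when L is above zero. So the rule leaves in the largest true losses, in understated form. Equally, keeping everyone would file some true losses as no worsening.

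**Reach.** The exclusion is from the analysis as a whole. The last-versus-worst shift table is built from two post-baseline values and needs no baseline, so valid data are lost there for no gain.

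**The case against.** The purpose is legitimate. An uncorrected baseline set against corrected follow-up hides real loss, and removing such baselines guards against understating toxicity. The proxy has some logic too: much on-treatment testing is prompted by symptoms, and acuity better than baseline during a corneal event makes a mismeasured baseline plausible. Under reading A the error overstates harm, the cautious direction for a safety table. All of this stands as a reason to exclude verified uncorrected baselines. It does not justify inferring them from the outcome.

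A reader might infer that everyone excluded belongs among those without worsening, so that the vision-loss rate is inflated. That needs reading A. The SAP does not say whether one value or all must beat baseline, or whether one eye or both, and it takes the worst result across eyes separately. Participants who worsened may therefore also be removed, while losses from retained uncorrected baselines pull the other way. The 20% in 6/30 is also not the true rate if some of those excluded really had uncorrected baselines.

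A reader might also think the tables uninterpretable or the toxicity assessment compromised. The tables are descriptive and no testing is planned (SAP 4.7). DLTs come from the eCRF DLT page (SAP 4.3.1.1). Corneal events are summarised from adverse-event data by grade, action taken, outcome, onset, recovery and recurrence (SAP 4.7.2). None of these uses the acuity exclusion.

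Lastly, the change log lists the visual acuity test among the SAP v2.0 updates. It does not say that this sentence was part of the update, so the documents do not show that the rule was written in response to observed values.

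**Conclusion.** The rule is wrong as written: a condition on post-baseline acuity stands in for a baseline measurement fault, and nothing else in either document supplies a recorded-method check, a count or an unrestricted table. It drops some correctly measured participants and keeps some mismeasured ones.

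The size cannot be computed from the documents. Under reading A, relative to keeping everyone, the factor N/(N-E) is about 1.1, 1.25 or 1.4 if 10%, 20% or 30% are excluded, and those shares are assumed. Under reading B the direction is open. Because uncorrected baselines also survive the rule with understated loss, the net bias is unknown under either reading. The consequence is confined to the descriptive visual-acuity tables, including a shift table that never needed the exclusion; the DLT, ORR and corneal-event analyses are unaffected.

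**What to change.** Replace the sentence in SAP 4.7.3.2 so that:
- an uncorrected baseline is identified from the recorded measurement method or a site query, never from on-treatment values;
- the exclusion applies only to tables that use the baseline value, so the last-versus-worst shift table keeps everyone;
- improvement in a participant with a valid baseline counts as no worsening;
- the number excluded is reported;
- where the method was not recorded, the tables are shown with and without the suspected participants. The rule for suspecting them should then state whether one or all values count and how the two eyes are handled.

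The eCRF is not among the documents, so the method may not have been recorded. In that case the paired tables and the count are the workable part. Since keeping everyone is not unbiased either, both versions are needed. The cost is one SAP sentence, possible site queries and one repeated safety table.
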